6.2.3 Tertiary outcomes analyses

Main analyses:

The analyses of the tertiary outcomes are descriptive and exploratory. We anticipate that many of these outcomes will occur infrequently, limiting our ability to conduct comprehensive multivariate analyses. Therefore, all analyses will be unadjusted and no sensitivity analyses will be conducted.

- The number of red blood cell units transfused per patient in the ICU will be analyzed using Student's t-test. We will report means, standard deviations, between-group difference and 95% CI. If data is not normally distributed, we will use the Wilcoxon rank sum test and report medians with interquartile ranges as well as median difference with 95% CI.
- The mean lowest daily Hb will be graphically displayed with associated 95% CI at each time point.
- The proportion of patients who had infections or transfusion complications will be analyzed using a Chi-square test. We will report an unadjusted RR.
- Duration of mechanical ventilation, as well as the length of stay in the ICU and the hospital, will be analyzed using the Wilcoxon rank sum test and reported with medians and interquartile ranges as well as median difference with 95% CI using quantile regression models.

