3.2 Randomization

Patients are randomized by the research coordinator using a secure, web-based, central, concealed, computerized randomization portal to allocate patients in a 1:1 ratio to either a liberal (experimental) or a restrictive (control) RBC transfusion strategy. Randomization is done with variable permuted blocks of 4 and 6, stratified by site. Staff members of the Ottawa Methods Centre of the Ottawa Health Research Institute (OHRI) who are not involved in the trial implementation generated the randomization sequence. Analysis of the primary and secondary outcomes will be done by biostatisticians blinded to the intervention. They will also carry out analyses of tertiary outcomes that can be performed without unblinding (i.e., infections, length of stay). Analyses of other tertiary outcomes that require unblinding or will inevitably lead to unblinding (i.e., transfusion-related complications, Hb levels, number of RBC units transfused) will be done by independent biostatisticians not involved in the blinded analyses of other outcomes.

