3.3 Sample Size

The sample size was calculated based on the proportion of patients who will experience an unfavourable outcome (i.e., GOSe ≤ 4 , which corresponds to upper severe disability). Assuming a 40% risk of unfavourable outcome in the control group^{5,6}, a sample size of 712 patients was originally estimated to detect an absolute risk reduction of 10% with a power of 80% and a type 1 error of 5%. This sample size calculation was conservative as it was based on the most widely-used definition of an unfavourable outcome in TBI using a simple dichotomous cut-off of the GOSe. Based on simulated data, the sliding dichotomy analysis is expected to increase the ability to observe the planned effect size with 95% power⁷. Initially, we had not adjusted the sample size for dropouts, given our experience with the prospective observational TBI-Prognosis study, where we did not encounter loss to follow-up when measuring a similar outcome using the same schedule.

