6.2 Analysis Methods

All analyses will be performed using the intention to treat principle (see Section 4.3). The main analysis for the primary and secondary outcomes will be adjusted for sex. It will also be adjusted for site, as there are expected variations in TBI mortality between centers, which may be explained in part by regional variations in approaches to discontinuation of life-sustaining therapies²⁰. All treatment effects and differences between groups will be reported with their corresponding 95% CIs. Analyses are summarized in [Table 1](#) and will be reported as outlined in [Appendix 2](#).

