6.2.1.3 Additional analyses of the primary outcome:

We will conduct additional analyses of the primary outcome to further assess the reliability of our results. Missing covariates will be handled as outlined in [section 6.3](#).

- Hierarchical proportional odds analysis. The regression model will be adjusted for site (random intercept), sex and admission covariates used in the TBI-IMPACT Prognostic model (age, GCS motor score, pupils, hypoxemia, hypotension, CT classification, tSAH and epidural mass on CT, glycemia and Hb).
- Robust hierarchical Poisson regression model for a dichotomized primary outcome (i.e., unfavourable outcome if the 6-month GOSe is ≤ 4). The model will be adjusted for site (random intercept), sex and admission covariates used in the TBI-IMPACT Prognosis model (age, GCS motor score, pupils, hypoxemia, hypotension, CT classification, tSAH and epidural mass on CT, glycemia and Hb).
- Chi-square test for a dichotomized primary outcome (i.e., unfavourable outcome if the 6-month GOSe is ≤ 4). We will also report a RR.

We will also perform sensitivity analyses of the additional analyses described above (i.e., proportional odds analysis and robust hierarchical Poisson regression model) by including only cases that have no missing covariates (i.e., complete case analysis).

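### SAP Section 6.2.3 leaves site out of the tertiary tests for a rarity reason that does not fit durations or RBC units; if sites differ, those tests are slightly conservative (minor)

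*SAP*

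**What the plan says.** SAP Section 3.2 makes site the randomisation stratum: "Randomization is done with variable permuted blocks of 4 and 6, stratified by site". Section 6.2 carries site into the main analyses of the primary and secondary outcomes: "It will also be adjusted for site, as there are expected variations in TBI mortality between centers".

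Section 6.2.3 treats the tertiary outcomes differently. It calls their analyses descriptive and exploratory, expects many of the outcomes to be uncommon, sees that as a limit on multivariate modelling, and concludes: "Therefore, all analyses will be unadjusted and no sensitivity analyses will be conducted". The tests, repeated in Table 1, are:

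- RBC units: t-test, or Wilcoxon if the data are not normal.
- Infections and transfusion complications: chi-square with an unadjusted risk ratio.
- Ventilation time, ICU stay and hospital stay: Wilcoxon, with quantile regression for the median difference.
- Lowest daily haemoglobin: plotted with confidence intervals, not tested.

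Section 4.1 applies the 0.05 level to all outcomes, and the shell of Table 3 in Appendix 2 reports tertiary effects with 95% intervals.

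**The concern.** The stated reason does not carry the decision. Ventilation time, the two lengths of stay and RBC units are quantities, not rare events. Rarity also argues against models with many covariates. A van Elteren or Cochran-Mantel-Haenszel test stratified by site fits no covariates and copes with sparse strata. The SAP already has a suitable tool: Section 6.2.2.1 plans quantile mixed models with a random intercept for site when secondary outcomes are skewed, while Section 6.2.3 uses quantile regression for durations without site.

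Blocking within site balances the arms within each site, so between-site variation largely drops out of the arm difference. An unstratified test still counts that variation as error. If sites differ in the outcome, the test rejects less often than its nominal level, the interval is wider than it needs to be, and some power is given away. Infections are the place where this would matter most, because a conservative test makes a real excess easier to miss.

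**Working it through.** **Inputs.** From the SAP: 1:1 allocation, blocks of 4 and 6 within site (3.2); 40% against 30%, 80% power, 5% level (3.3); 742 patients after allowing for 2% dropout (3.5); 0.05 level for all outcomes (4.1). Two-sided tests are assumed. The SAP states neither the number of sites nor the share of outcome variance due to site (rho), so both are assumptions shown over a range.

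**Step 1: the plan's own figure.** n per arm = [1.96·√(2·0.35·0.65) + 0.8416·√(0.4·0.6 + 0.3·0.7)]² / 0.10² = (1.3221 + 0.5646)² / 0.01 ≈ 356, so 712 in total, as in "a sample size of 712 patients was originally estimated". Then 712/0.98² = 741.4, giving 742. Both reproduce. They serve here only to anchor a test with 80% power.

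**Step 2: large-sample approximation.** With balance within sites, the true standard error is √(1−rho) times the one that the unadjusted test uses. With 1.96 + 0.8416 = 2.8016:

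- size, unadjusted = 2·[1 − Φ(1.96/√(1−rho))]
- power, unadjusted = Φ(0.8416/√(1−rho))
- power, site-adjusted = Φ(2.8016/√(1−rho) − 1.96)
- interval width, unadjusted relative to adjusted = 1/√(1−rho)

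| rho | Size, unadjusted | Power, unadjusted vs adjusted | Points forgone | Width ratio |
|---|---|---|---|---|
| 0 | 5.00% | 80.0 vs 80.0% | 0 | 1.00 |
| 0.02 | 4.77% | 80.24 vs 80.79% | 0.55 | 1.01 |
| 0.05 | 4.43% | 80.61 vs 81.97% | 1.36 | 1.03 |
| 0.10 | 3.88% | 81.25 vs 83.97% | 2.72 | 1.05 |
| 0.20 | 2.84% | 82.66 vs 87.95% | 5.29 | 1.12 |

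**Step 3: simulation.** 728 patients (about 742 × 0.98 = 727), 20 sites of uneven size, blocks of 4 and 6. The binary outcome takes the Section 3.3 rates as a stand-in for a common event (4,000 replicates for size, 2,000 for power). Durations are log-normal, rounded up to days (4,000 replicates). Monte Carlo error is about 0.3 points for size and 0.6 to 0.9 for power.

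| Outcome and tests | rho | Size, unstratified vs stratified | Power, unstratified vs stratified |
|---|---|---|---|
| Durations, Wilcoxon vs van Elteren | 0.02 | 5.4 vs 5.4% | 79.4 vs 79.1% |
| | 0.05 | 4.5 vs 4.8% | 79.9 vs 80.5% |
| | 0.10 | 3.8 vs 4.7% | 79.9 vs 81.5% |
| | 0.15 | 3.8 vs 5.1% | 81.7 vs 84.9% |
| | 0.20 | 3.1 vs 4.9% | 81.2 vs 85.8% |
| Binary, chi-square vs Cochran-Mantel-Haenszel | 0.05 | 4.5 vs 5.0% | 82.3 vs 83.3% |
| | 0.10 | 3.7 vs 4.6% | 81.2 vs 83.0% |
| | 0.20 | 3.1 vs 5.3% | 81.4 vs 85.7% |

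With 34 sites and rho 0.05, the binary results were 4.5 vs 5.0% for size and 83.1 vs 84.3% for power. A further run for durations with 742 patients and 30 sites gave no gain at 0.05, equal power at 0.10 (size 4.4%), and 79.1 vs 83.0% at 0.15 (size 3.8%). So gains at low rho are close to the limit of what these simulations can resolve.

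**Step 4: rare events.** For a binary outcome with rate p and a site standard deviation s on the logit scale, rho is roughly p(1−p)s². At s = 0.6 this is 0.35·0.65·0.36 ≈ 0.08 for a 35% event, but 0.05·0.95·0.36 ≈ 0.017 for an assumed 5% event. By Step 2, the latter costs about half a power point.

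**The case against.** The tertiary analyses are declared exploratory, and the notes to Table 3 in Appendix 2 warn that the intervals carry no multiplicity adjustment and that inferences may not be reproducible. Any error is on the conservative side, and no main conclusion depends on these tests. This stands, and it keeps the point minor. It does not repair the reason given, because Section 4.1 still tests these outcomes at 0.05 and the remedy costs almost nothing.

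Three stronger readings are tempting, and the SAP does not support them.

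- A reader might infer that the tests are conservative as a matter of fact. Section 6.2 asserts variation between centres for mortality only. It is plausible that ventilation and stay also vary, since Section 6.2 links the mortality differences to practice in discontinuing life support, but that is inference. With no site variation there is no loss, and at a share of 0.05 or below the loss is negligible.
- A reader might extend the point to the "Chi-square test for a dichotomized primary outcome" in Section 6.2.1.3. The rarity reason is not given there. That test is listed directly after a Poisson model of the same GOSe ≤4 endpoint with a site random intercept, so inference does not rest on it. It is a legitimate unadjusted companion.
- A reader might take the point to cover every tertiary outcome. Lowest daily haemoglobin has no test to stratify, and for rare complications and rare infections Step 4 shows almost nothing to gain.

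**Conclusion.** The point holds in conditional form and is minor. The infrequency argument does not justify leaving the randomisation stratum out of the comparisons of ventilation time, stays and RBC units, and it does not exclude simple stratified tests for the commoner infections.

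If sites differ, true size is about 4.5% at a site variance share of 0.05, 3.8% at 0.10 and 3.1% at 0.20. The power forgone is about 0.5 to 1.5, 1.5 to 3 and 4 to 5 points respectively, although one of the simulated settings showed none at 0.05 and 0.10. By the approximation in Step 2, intervals are about 3%, 5% and 12% wider than needed. For RBC units, interval width is the main issue, because the two strategies are built to differ in transfusion.

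These figures rest on assumed site numbers, site variance shares and outcome distributions. Type I error is not inflated and the primary conclusion is unaffected.

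**What to change.** In Section 6.2.3 and Table 1, replace the blanket statement that tertiary analyses are unadjusted with the following:

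- **Ventilation time, ICU stay, hospital stay:** van Elteren (site-stratified Wilcoxon) test, with site included in the quantile regression behind the median difference.
- **RBC units:** include site in the comparison, through a linear model with site in place of the t-test, or the van Elteren test with site in the model for the median difference if the data are not normal.
- **Commoner infection outcomes:** Cochran-Mantel-Haenszel test with a Mantel-Haenszel risk ratio, stratified by site, pooling very small sites within country.
- **Rare transfusion complications and rare infections:** keep unadjusted reporting, and confine the infrequency reason to these.
- **Lowest daily haemoglobin plot and GOSe ≤4 chi-square:** no change.

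The SAP should also state in advance the event count that separates commoner from rare infections and the rule for pooling sites. The cost is a wording change and different procedure calls. Very small sites will contribute little to the stratified tests. If allocation has already been unblinded, the stratified results should be labelled post hoc.

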4.3 Analysis populations

Intention-to-treat population. This population includes all randomized TBI patients except those who withdrew consent or were lost to follow-up. Baseline characteristics for the intention-to-treat population will be reported in the main manuscript.

Per-protocol population: This population includes all patients within the intention-to-treat group, except those who were allocated to the liberal strategy but were not transfused within a 24-hour time window after reaching Hb ≤ 100 g/L (protocol violation category #3), and those who were allocated to the restrictive strategy but were transfused despite not reaching their transfusion threshold of ≤ 70 g/L, or received more than one unit without reassessing the Hb despite the absence of ongoing important bleeding (protocol violation category #1 and 2). Baseline characteristics for the per-protocol population will be reported in an online Supplementary Appendix.

For the patients included and excluded from the per-protocol population, the median time to transfusion and the mean pretransfusion Hb level will be reported according to the treatment allocation.

Section 5 – Trial Population

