6.1.2 Secondary outcomes

- All-cause mortality at ICU discharge, at hospital discharge, and at 6 months.
- Functional independence will be assessed using the FIM. This scale evaluates the amount of assistance required to perform 18 basic daily activities (13 physical and five cognitive components)¹⁵. Each component is scored on a 7-point scale. The final score ranges from 18 to 126, where 18 represents complete dependence and 126 represents complete independence. Deceased patients will be removed for the main analysis.
- Quality of life will be assessed using the Visual Analogue Scale (VAS) of the EQ-5D-5L questionnaire¹⁶. The EQ-VAS is a generic self-assessment instrument for health-related quality of life, for which zero and 100 represent the worst and best imaginable state of health, respectively. Deceased patients will be removed for the main analysis.

- Quality of life will also be assessed using the QOLIBRI questionnaire¹⁷. The scores are reported on a 0-100 scale, with zero being the worst possible quality of life and 100 being the best possible quality of life. Deceased patients will be removed for the main analysis.
- Depression will be assessed using the self-reported PHQ-9¹⁸, which includes nine items that assess the frequency of depressive symptoms in the past 2 weeks. The score lies between zero and 27 with zero being the best outcome and 27 the worst. A threshold value ≥ 10 is generally accepted as the standard for identifying major depression¹⁹. Deceased patients will be removed for the main analysis.

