6.1.3 Tertiary outcomes

- The number of red blood cell units transfused in the ICU.
- The lowest daily Hb level recorded in the ICU.
- Infections categorized as any infection, pneumonia, bacteremia, sepsis/septic shock, central nervous system infection. Both the proportion of patients who had an infection and the proportion of patients who had each category of infection.
- The length of time spent on mechanical ventilation in the ICU.
- The length of stay in the ICU.
- The length of stay in the hospital.
- Complications of red blood cell blood transfusions.

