Median length of hospital stay — days (interquartile range)¶	9.9 (0.0 to 9.9)	9.9 (0.0 to 9.9)	x.xx (y.yy to z.zz)

* Plus-minus values are means ±SD.

† Confidence intervals have not been adjusted for multiplicity, and inferences drawn from the intervals may not be reproducible.

‡ Secondary outcomes were centrally assessed by blinded trained personnel. All analyses are adjusted for site (random intercept), sex and admission covariates used in the TBI-IMPACT Prognosis model (age, motor score, pupils, hypoxemia, hypotension, CT classification, traumatic SAH on CT, epidural mass on CT, glycemia and Hb)

§ In this category, the treatment effect is a hazard ratio.

¶ In this category, the treatment effect is the between-group difference.

|| The Functional Independence Measure scale evaluates the amount of assistance required to perform 18 basic daily activities (13 physical and five cognitive components). Each component is scored on a 7-point scale. The final score ranges from 18 to 126, where 18 represents complete dependence and 126 represents complete independence. Patients who died or with missing data were excluded (xx in the Liberal Strategy and yy in the Restrictive Strategy).

** The EuroQoL 5-Dimension 5-Level Visual Analogue Scale is a generic instrument for health-related quality of life, for which zero and 100 represent the worst and best imaginable state of health, respectively.

†† The Quality of Life after Brain Injury Scale is a TBI-specific instrument for health-related quality of life, for which zero and 100 represent the worst and best imaginable state of health, respectively.

[figure not shown]
‡‡ Patient Health Questionnaire includes nine items that assess the frequency of depressive symptoms in the past 2 weeks. The score lies between zero and 27 with zero being the best outcome and 27 the worst.

§§ Tertiary outcomes were assessed locally by unblinded trained research personnel using standardized definitions.

¶¶ From the randomization to the ICU discharge

||| In this category, the treatment effect is a risk ratio

*** Detailed description of transfusion reactions is provided in the Supplementary Appendix.

Figure 2. Levels on the Glasgow Outcome Scale-extended at 6 Months.

Appendix 3

Interpretation of head CT scans results

We used a rigorous 3-step approach to ensure a robust and unbiased assessment of head CT scans.

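### No rule is given for deaths in ventilation time, ICU stay and hospital stay, so by default a death enters as a completed, often short, duration

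*SAP*

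**What the plan says.** SAP section 6.1.3 names three raw durations: "The length of time spent on mechanical ventilation in the ICU", "The length of stay in the ICU", and the corresponding hospital stay. Section 6.2.3 compares all three by rank sum test ("as well as the length of stay in the ICU and the hospital, will be analyzed using the Wilcoxon rank sum test") and reports medians, interquartile ranges and a quantile-regression median difference with a 95% CI. It adds: "Therefore, all analyses will be unadjusted and no sensitivity analyses will be conducted".

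On who is analysed, section 6.2 says "All analyses will be performed using the intention to treat principle (see Section 4.3", and section 4.3 defines that population: "This population includes all randomized TBI patients except those who withdrew consent or were lost to follow-up". Patients who die are therefore kept.

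A rule for the deceased exists only for FIM, EQ-VAS, QOLIBRI and PHQ-9 in section 6.1.2: "Deceased patients will be removed for the main analysis". In Table 3 of Appendix 2 the FIM footnote repeats that exclusion. The three duration rows, for example "Median length of hospital stay — days (interquartile range", carry no note about deaths. Section 4.1 sets the 0.05 significance level for every outcome, and section 6.2.3 calls the tertiary analyses descriptive and exploratory.

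**The concern.** Death ends ventilation, ICU stay and hospital stay just as extubation and discharge do, but it means the opposite. If death is simply the end of the duration, a patient who dies on day 3 gets a lower rank than one discharged on day 10. A between-arm difference in early mortality then turns into a between-arm difference in duration, and the arm with more deaths looks shorter.

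Mortality is a secondary outcome that the trial expects may differ by strategy, so this is not remote. The duration rows will stand in the main results table with an effect estimate and a confidence interval. Because section 6.2.3 rules out sensitivity analyses for tertiary outcomes, nothing planned would separate a faster recovery from earlier deaths.

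**Working it through.** **Reading the rules together.** Section 6.1.3 gives raw durations, section 6.2.3 a rank test without censoring, and sections 6.2 and 4.3 a population that includes deaths. Section 6.1.2 removes the deceased for other outcomes only. For the three durations the SAP mentions no censoring, competing-event method, worst rank, ventilator-free days or split by survival status. The default is that a death contributes the time observed up to death.

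**Figures in the plan.** There is none for durations. The sample size supplies the arm size used below, so it was checked first. With 40% v 30%, two-sided 5%, 80% power and pooled variance:

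n = [1.96·√(2·0.35·0.65) + 0.8416·√(0.40·0.60 + 0.30·0.70)]² / 0.10² = 355.9, so 356 per arm and 712 in total. Then 712/(1 − 0.02)² = 741.4, raised to 742. Both stated figures reproduce. With 2% dropout, 742 × 0.98 / 2 = 363.6, so 364 per arm is used.

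**How mortality enters the rank test.** Let p₁ and p₂ be mortality in the two arms, with survivors' stays distributed identically in both arms and deaths' stays likewise. Let θ be the probability that a death's duration is shorter than a survivor's. Then

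P(arm 1 stay < arm 2 stay) = ½ + (p₁ − p₂)(θ − ½).

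The shift is zero if p₁ = p₂ or if θ = ½. For log-normal durations with log SD 0.8, θ = Φ[ln(survivor median / death median) / (0.8·√2)]. The null standard error is √[(2·364 + 1)/(12·364²)] = 0.0214. The chance that arm 1 is significantly shorter is about Φ(shift/0.0214 − 1.96).

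All medians and mortality rates below are assumptions. The simulations used 1,500 trials per row and no difference in survivors' duration.

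| Assumed medians, survivors / deaths | Mortality | θ | Shift | Formula | Simulated | Median difference |
|---|---|---|---|---|---|---|
| ICU, 14 / 6 days | 20% v 20% | 0.773 | 0 | 2.5% | 2.7% | −0.1 d |
| | 25% v 20% | 0.773 | 0.0137 | 9.3% | 10.3% | −0.5 d |
| | 30% v 25% | 0.773 | 0.0137 | 9.3% | 8.9% | −0.5 d |
| | 30% v 20% | 0.773 | 0.0273 | 24.7% | 24.3% | −1.0 d |
| Hospital, 35 / 7 days | 20% v 20% | 0.923 | 0 | 2.5% | 2.3% | 0.0 d |
| | 25% v 20% | 0.923 | 0.0211 | 16.5% | 16.3% | −2.0 d |
| | 30% v 25% | 0.923 | 0.0211 | 16.5% | 16.1% | −1.9 d |
| | 30% v 20% | 0.923 | 0.0423 | 50.5% | 49.1% | −3.9 d |
| Late deaths, 14 / 14 days | same four pairs | 0.500 | 0 | 2.5% | 2.4 to 2.9% | about 0 |

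The percentages are the share of trials in which the arm with more deaths is significantly shorter; the nominal rate in that direction is 2.5%.

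**Sensitivity to the assumptions.** Further runs kept survivors at a median of 14 days.

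- At 33% v 25% mortality, the rate is 30% with deaths at a median of 4 days and 14% with deaths at 7 days.
- Near-null cases, as two-sided rejection against a nominal 5%: with deaths at 10 days, 5.7% (30% v 25%) and 7.3% (33% v 25%); with deaths at 4 days, 7.3% (27% v 25%).

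Ventilation time was not simulated separately. The same formula applies to it with its own medians.

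**Alternatives, in the runs tabulated above.** With mortality unequal, ranking deaths worst cuts significance in favour of the arm with more deaths to 0.1% or less. At 30% v 20%, however, it rejects in the other direction in 63% (ICU) and 65% (hospital) of trials with no difference among survivors, so it largely re-tests mortality. A survivors-only test stays at 2.1 to 3.0% but conditions on a post-randomization event.

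**The case against.** Three stronger readings are tempting, and the SAP supports none of them.

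- *The plan counts deaths as short, better results.* It does not say so. The counting of deaths is inferred from the population rule and the absence of any other rule, and the SAP nowhere calls a shorter stay a benefit. As a measure of days used, an all-patient duration that includes deaths is legitimate.
- *The test is invalid.* When mortality differs, the two distributions of duration really do differ, so the rejections above are not type I errors of the Wilcoxon test. The problem is what the difference would be taken to mean.
- *The plan saw the problem for the secondary scores and ignored it here.* FIM, quality-of-life and depression scores do not exist for patients who have died, whereas durations do. Removing the deceased in section 6.1.2 does not show awareness of a ranking problem.

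Other mitigation is real. The analyses are labelled exploratory, Table 3 warns that its intervals are not adjusted for multiplicity, and ICU, hospital and 6-month mortality stand in the same table. Section 3.1 says tertiary outcomes follow standardized definitions, and a document not shown might define when a duration ends.

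What remains is that the way a death enters a rank test is an analysis decision that belongs in the SAP. The exploratory label lowers the weight of the result but does not tell a reader whether a shorter stay reflects discharge or death.

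**Conclusion.** The concern holds as a gap with a predictable consequence. No death rule is stated for the three durations. Followed as written, the plan lets deaths in as completed durations, and a difference in early mortality can appear as a shorter duration with no effect in survivors. No planned sensitivity analysis would reveal it.

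The size rests wholly on assumed mortality and timing of death. It runs from nothing (equal early mortality, or deaths as late as discharge) to 49% of trials in the most extreme tabulated case (hospital stay, 30% v 20% mortality, deaths at a median of 7 days against 35 for survivors). The direction is fixed whenever the arm with more deaths has them earlier than survivors' discharge. Severity is minor: the outcomes are tertiary and exploratory, and neither the primary analysis nor any sample-size figure is affected.

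**What to change.** In section 6.2.3 and Table 3 of Appendix 2:

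1. Keep the all-patient median (IQR) as a description of resource use, labelled as including patients who died.
2. Add the median (IQR) separately for survivors and non-survivors, as description only.
3. Base the between-arm comparison on the cumulative incidence of extubation alive, ICU discharge alive and hospital discharge alive, with death as a competing event. State the time origin and horizon.
4. Optionally, give a Wilcoxon test with deaths ranked worst as a supplementary analysis, with a note that it combines death and duration.

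State the rule in section 6.1.3 as well, so that outcome definition and analysis agree.

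The cost is SAP wording, a few extra table rows and a small amount of programming. Dates of death are already needed for the planned frailty models and Kaplan-Meier curves, and the durations are already collected. The cumulative incidence of discharge alive also responds to mortality, but more deaths then count against an arm. The survivor and non-survivor medians should stand beside it.
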